2. SCHEDULE OF ACTIVITIES (SoA)	
 • Drug screen was previously mentioned at footnote 'a' of SoA table. An additional line of urine drug screen is added to the main table. • An additional line of Urine chemistry assessment at day 1 is added for baseline assessment • Additional line for oral phase diary card at day 1. • Updated footnote 'n': All PK samples will be collected prior to CAB LA injections at Week 5, 9, 17, 25, and 33 with the exception of 1-week post injection samples at Weeks 6, 10, 18, 26, 34, week 37(2-4-week post injection sample) and Week 41 	
 • Added for more clarity • It is added since, Appendix 4 Adverse Events- Proteinuria mentioned that, 'change from Baseline value for abnormal urine microalbumin/creatinine ratio' • Additional assessment • Updated the schedule PK sampling post injection
5.1. Overall Design	4 PK Pharmacokinetic sampling following CAB LA IM injections will start on just prior to the first injection at Week 5 (Injection Phase) and prior to each subsequent injection with limited PK sampling between injection visits (for complete PK sampling schedule refer to SoA, Table 1).	Added for more clarity
7.1.3. GSK1265744 – Injectable Suspension (CAB LA)	IM injections should be administered at a 90 degree angle into the gluteus medius muscle using a 1.5" – 2.5" 21-25 gauge needle (or sizes outside of this suggested range based on investigator judgement)	Text added around the dimensions of injection needle use for CAB LA injection
7.6. Treatment Compliance	CAB LA dosing is expected to occur in a window ± 3 Days any time within the scheduled dose week.	Mentioned the specific window period for CAB LA dosing
8.1. Discontinuation of Study Treatment	Participants who discontinue treatment during the injection phase should enter the be followed up phase for at least 56 weeks after their last injection as per	Minor edits for more clarity

Section # and Name	Description of Change	Brief Rationale
	the schedule of activities.	

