2. SCHEDULE OF ACTIVITIES (SOA)

Table 1 SCHEDULE OF ACTIVITIES^a

Clinical Assessments	Screening ^a	Oral Phase ^m		Injection Phase												Follow-up Phase & Final Visit	
		Day 1	Day 28 (Week 4)	Day 35 (Week 5) Injection 1	Day 42 (Week 6)	Week 9 Injection 2	Week 10	Week 17 Injection 3	Week 18	Week 25 Injection 4	Week 26	Week 33 Injection 5	Week 34	Week 37	Week 41	Week 53, 65, 77	Week 89
Written informed consent	X																
Inclusion/Exclusion criteria ^b	X																
Demographic information	X																
Full physical exam/medical history ^c	X																X
Brief physical exam		X	X	X	X	X	X	X	X	X	X	X	X	X	X		
Height/weight/BMI ^d	X																X
Medication/drug/alcohol history	X																
HIV counseling	X	X	X	X	X	X	X	X	X	X	X	X	X	X	X	X	X
Offer condoms and lubricant	X	X	X	X	X	X	X	X	X	X	X	X	X	X	X	X	X
Dispense oral study medication (with counseling) ^e		X															
Drug accountability (pill counts)		X	X														
CAB LA Injection (with counseling)				X		X		X		X		X					
HIV-PrevTSC ^f							X										
Oral phase diary card		X															

Clinical Assessments	Screening ^a	Oral Phase ^m		Injection Phase												Follow-up Phase & Final Visit	
		Day 1	Day 28 (Week 4)	Day 35 (Week 5) Injection 1	Day 42 (Week 6)	Week 9 Injection 2	Week 10	Week 17 Injection 3	Week 18	Week 25 Injection 4	Week 26	Week 33 Injection 5	Week 34	Week 37	Week 41	Week 53, 65, 77	Week 89
ISR AE Diary ^g				X		X		X		X		X					
AE		X	X	X	X	X	X	X	X	X	X	X	X	X	X	X	X
SAE review (SAE will be collected from the signing of ICF)	X	X	X	X	X	X	X	X	X	X	X	X	X	X	X	X	X
Concomitant medication check		X	X	X	X	X	X	X	X	X	X	X	X	X	X	X	X
Vital signs ^h	X	X		X	X	X	X	X	X	X	X	X	X	X	X	X	X
Qualitative HIV RNA by NAAT ⁱ	X																
HIV PoC test ^j	X	X		X		X		X		X		X			X	X	X
ECG ^k	X																
HbsAg and HbsAb, HCV Antibody	X																
Hematology/Chemistry testing	X	X	X	X	X	X		X		X		X			X		X
Urinalysis	X														X		
Urine drug screen	X																
Urine chemistry		X															
Urine screen for Chlamydia and gonorrhea	X																
Liver Chemistry Tests ^l																X	
Fasting lipid profile		X													X		
Coagulation testing	X														X		

Clinical Assessments	Screening ^a	Oral Phase ^m		Injection Phase												Follow-up Phase & Final Visit		

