12.2. Appendix 2: Clinical Laboratory Tests

- The tests detailed in [Table 5](#) will be performed by the central laboratory.
- Local laboratory results are only required in the event that the central laboratory results are not available in time for either study treatment administration and/or response evaluation. If a local sample is required, it is important that the sample for central analysis is obtained at the same time.
- Protocol-specific requirements for inclusion or exclusion of participants are detailed in [Section 6](#) of the protocol.
- Additional tests may be performed at any time during the study as determined necessary by the investigator or required by local regulations.

Table 5 Protocol-Required Safety Laboratory Assessments

Laboratory Assessments	Parameters			
Hematology	Platelet Count	RBC Indices: MCV MCH % Reticulocytes MCHC		WBC count with Differential : Neutrophils Lymphocytes Monocytes Eosinophils Basophils
	RBC Count			
	Hemoglobin			
	Hematocrit			
	WBC Count (absolute)			
	Reticulocyte Count			
Clinical Chemistry ^{1,2}	BUN	Potassium	Aspartate Aminotransferase (AST)/ Serum Glutamic-Oxaloacetic Transaminase (SGOT)	Total and direct bilirubin
	Creatinine	Sodium	Alanine Aminotransferase (ALT)/ Serum Glutamic-Pyruvic Transaminase (SGPT)	Total Protein
	Glucose non fasting except for day 1 and week 41	Calcium	Alkaline phosphatase	Creatine phosphokinase (CPK)
	Total CO ₂	Gamma glutamyltransferase (GGT)	Calculated creatinine clearance – Cockcroft-Gault equation	Uric Acid

Laboratory Assessments	Parameters			
	Albumin	Chloride	Glomerular Filtration Rate (GFR)	phosphate
	Lactate Dehydrogenase (LDH)			
Lipid Panel ²	Total Cholesterol	High-density lipoprotein (HDL)	Low Density Lipoprotein (LDL)	Triglyceride
Coagulation Panel	Prothrombin Time (PT)	PTT	International normalized ratio (INR)	
Routine Urinalysis	
 • Specific gravity • pH, glucose, protein, blood, ketones, (bilirubin, urobilinogen, nitrite, leukocyte esterase) by dipstick • Microscopic examination (if blood or protein is abnormal) 			
Urine Chemistry	
 • Microalbumin • Creatinine • Microalbumin/creatinine ratio 			

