Participants who have a decline in the estimated GFR (using the CKD-EPI method) of $>50\%$ from Baseline must return for a confirmatory assessment as soon as possible [Levey, 2009]. A urinalysis and urine albumin/creatinine and urine protein/creatinine ratios should also be done at this confirmatory visit. If the estimated GFR has declined by $>50\%$ (confirmed), then study drug should be withheld and the investigator should contact the study medical monitor to discuss the rationale for restarting study drugs (if appropriate). Consideration for confounding factors (e.g., background therapy, other medications, dehydration, and concurrent conditions) should be taken into account, and a nephrology consult may be obtained.

Proximal Renal Tubule Dysfunctions

Proximal Renal Tubule Dysfunctions (PRTD) is defined as:

Confirmed rise in serum creatinine of ≥ 0.5 mg/dL from Baseline AND serum phosphate < 2.0 mg/dL ;

Either of the above accompanied by any two of the following:

Glycosuria (≥ 250 mg/dL) in a non-diabetic;

Low serum potassium (< 3 mEq/L);

Low serum bicarbonate (< 19 mEq/L).

Participants meeting criteria for PRTD must return for a confirmatory assessment within 2 weeks of diagnosis. A urinalysis should also be performed at the time of the confirmatory assessment. If PRTD is confirmed participants should have study drug withheld and the investigator should contact the Study medical monitor to discuss the rationale for restarting study drugs (if appropriate). Consideration for confounding factors (e.g. other medications, dehydration, concurrent conditions) should be taken into account, and a nephrology consult may be obtained.

Proteinuria

Participants with an abnormal urine microalbumin/creatinine ratio (>0.3 mg/mg, >300 mg/g, or >34 mg/mmol) that represents a change from Baseline and no associated increase in creatinine, should have a repeat spot urine microalbumin/creatinine ratio performed within 2-4 weeks. If confirmed, then consideration should be given to additional evaluation after consultation with the study medical monitor. Additional evaluation may include a 24-hour urine protein and creatinine measurement and nephrology referral.

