Participants with an abnormal urine albumin/creatinine ratio (>0.3 mg/mg, 300 mg/g, or >34 mg/mmol and representing a change from Baseline) and a serum creatinine increase >45 $\mu\text{mol/L}$ (or 0.5 mg/dL) should have confirmation of both results within 2 weeks. If confirmed, the study medical monitor should be contacted immediately. Agreement on further management should be agreed between the investigator and medical monitor.

Definition of SAE

If an event is not an AE per definition above, then it cannot be an SAE even if serious conditions are met (e.g., hospitalization for signs/symptoms of the disease under study, death due to progression of disease).

A SAE is defined as any untoward medical occurrence that, at any dose:

a. Results in death

b. Is life-threatening
 
The term 'life-threatening' in the definition of 'serious' refers to an event in which the participant was at risk of death at the time of the event. It does not refer to an event, which hypothetically might have caused death, if it were more severe.

c. Requires inpatient hospitalization or prolongation of existing hospitalization
 
In general, hospitalization signifies that the participant has been detained (usually involving at least an overnight stay) at the hospital or emergency ward for observation and/or treatment that would not have been appropriate in the physician's office or outpatient setting. Complications that occur during hospitalization are AE. If a complication prolongs hospitalization or fulfils any other serious criteria, the event is serious. When in doubt as to whether "hospitalization" occurred or was necessary, the AE should be considered serious.
 
Hospitalization for elective treatment of a pre-existing condition that did not worsen from baseline is not considered an AE.

d. Results in persistent disability/incapacity
 
 • The term disability means a substantial disruption of a person's ability to conduct normal life functions. • This definition is not intended to include experiences of relatively minor medical significance such as uncomplicated headache, nausea, vomiting, diarrhea, influenza, and accidental trauma (e.g., sprained ankle) which may interfere with or prevent everyday life functions but do not constitute a substantial disruption.

e. Is a congenital anomaly/birth defect

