7.1.3. Clinical Laboratory Tests

All clinical laboratory tests will be graded according to the [Appendix 7](#) from the study protocol. Grade 2 or higher laboratory events will be tabulated by number and percentage of subjects with the event by study phase.

Change from baseline in hematology, fasting chemistry, fasting lipid profile, and coagulation profile will be summarized by visit. For the definition of baseline, refer to Section [10.5.2](#). Urinalysis and urine chemistry results will be summarized by visit as either categorical values or as continuous values, depending on the type of the parameter.

For each lab test, shift from baseline table will be provided based on toxicity grade, both by visit and for the shift to maximum toxicity grade in each study phase. Data collected at unscheduled visits will not be included in the by-visit summary, but will be used in the calculation of maximum grade in each study phase. Subjects having both high and low values will be counted in both High and Low categories for the summary by study phase.

All lab data, as well as lab data for subjects with Grade 2 or higher abnormalities, will be listed. Abnormal data will be listed with an indicator, which is low/high relative to normal range. All laboratory results from local labs, if any, will be listed only

[Table 5](#) provides an overview of the planned lab test analyses, with full details of data displays being presented in [Appendix 14](#): List of Data Displays.

Table 5 Overview of Planned Lab Test Analyses

Display Type	Absolute				Change from Baseline			
	Summary		Individual		Summary		Individual	
	T	F	F	L	T	F	F	L
Laboratory Test Analyses								
Grade 2 or high laboratory events	Y							
Clinical Chemistry				Y	Y			
Hematology				Y	Y			
Fasting Lipid Profile				Y	Y			
Coagulation Profile				Y	Y			
Urinalysis and Urine Chemistry	Y			Y	Y			
Other lab data including local lab				Y				

- T = Table, F = Figure, L = Listing, Y = Yes display generated.
- Stats Analysis = Represents TFL related to any formal statistical analyses (i.e. modelling) conducted.
- Summary = Represents TFL related to any summaries (i.e. descriptive statistics) of the observed raw data.
- Individual = Represents FL related to any displays of individual subject observed raw data.

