10.5.2. Baseline Definition & Derivations

10.5.2.1. Baseline Definitions

The baseline or pre-dose assessment is the last available assessment prior to the time of the first dose unless it is specified otherwise.

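### No urine microalbumin/creatinine ratio is scheduled after Day 1, so a rise without a creatinine rise can be found only by a discretionary test

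*Protocol*

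**What the plan says.** Protocol Appendix 4 (12.4) lists proteinuria among the adverse events of special interest and gives two branches. The first concerns a urine microalbumin/creatinine ratio above 300 mg/g "that represents a change from Baseline and no associated increase in creatinine"; it calls for a repeat ratio within 2 to 4 weeks. The second pairs an abnormal ratio, again "and representing a change from Baseline", with a serum creatinine increase above 45 µmol/L, and asks for both to be confirmed within 2 weeks.

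In Protocol Table 1 the row "Urine chemistry" has one mark, at Day 1. The summary of changes gives its purpose: "assessment at day 1 is added for baseline assessment". Protocol Table 5 (Appendix 2) puts the item "Microalbumin/creatinine ratio" in the urine chemistry panel only. Routine urinalysis, scheduled at Screening and Week 41, covers "pH, glucose, protein, blood, ketones, (bilirubin, urobilinogen, nitrite, leukocyte esterase) by dipstick", plus specific gravity and conditional microscopy. It gives no ratio.

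On analysis, SAP 7.1.3 states: "Urinalysis and urine chemistry results will be summarized by visit as either categorical values or as continuous values". SAP Table 5 also marks a change-from-baseline summary for urinalysis and urine chemistry as one combined row. SAP 10.5.2.1 sets the baseline: "The baseline or pre-dose assessment is the last available assessment prior to the time of the first dose". SAP 2.1 keeps proteinuria as an event of special interest, and SAP 10.16 identifies it by narrow terms of the MedDRA proteinuria query. The SAP's copy of the schedule (Table 21) has no urine chemistry row.

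**The concern.** A rule that depends on change from baseline needs a baseline and at least one later value. The amendment supplied the baseline. The request for a repeat ratio presupposes an abnormal post-baseline ratio, and no visit is scheduled to produce one. The branch without a creatinine rise is the most exposed, because serum chemistry cannot prompt the urine test there.

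The stake is interpretation of the safety report. Clinical laboratory tests are part of the primary safety endpoint. A report with Day 1 ratios and no scheduled comparator, beside a low proteinuria count, could be read as evidence that the ratio did not rise. It would only show that the ratio was not routinely measured.

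**Working it through.** The plan states no figure to reproduce. The check is a count of scheduled tests, followed by a trace of each route to a post-baseline ratio.

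**Scheduled visits after Day 1.** Protocol Table 1 has 17 columns. Removing Screening and Day 1 leaves 17 − 2 = 15. One of these holds three visits (Weeks 53, 65 and 77), so the number of visits is 15 + 2 = 17.

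| Test | Visits after Day 1 | Count |
|---|---|---|
| Urine chemistry (the ratio) | none | 0 of 17 |
| Urinalysis (dipstick protein) | Week 41 | 1 of 17 |
| Serum chemistry (creatinine) | Day 28; Weeks 5, 6, 9, 17, 25, 33, 41, 89 | 9 of 17 |

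Scheduled change-from-baseline values for the ratio are therefore 0 per participant, although about 48 participants entering the oral phase would have a Day 1 value.

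**Routes to a post-baseline ratio outside the schedule.**

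1. *Creatinine rise.* The renal function text in Appendix 4 asks for a urine albumin/creatinine ratio at the confirmatory visit after a rise of 45 µmol/L. This feeds the second branch and has nine scheduled opportunities to be triggered.
2. *Fall in estimated GFR of more than 50%.* This also leads to a ratio at a confirmatory visit. I assume that the CKD-EPI estimate is the serum creatinine form, so that such a fall implies a creatinine rise.
3. *Discretion.* Appendix 2 lets the investigator add tests at any time.

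Routes 1 and 2 do not serve the branch without a creatinine rise. Only route 3 does.

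**Consequence in the SAP.** SAP 7.1.3 keeps unscheduled data out of by-visit laboratory summaries, and SAP 10.5.3 keeps unscheduled visits out of summary tables. For-cause ratios would appear in Listing 27 but not in Table 2.20. The urine chemistry rows of Table 2.20 would show Day 1 only; its urinalysis rows would still have Week 41. For urine chemistry, the change-from-baseline mark in SAP Table 5 has no scheduled data behind it.

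**The case against.** The strongest reply is that the analysed event does not need the ratio. The SAP counts proteinuria from reported adverse events with MedDRA terms such as albuminuria, adverse events are collected at every visit from Day 1 to Week 89, and the Week 41 dipstick is graded under Appendix 7. All of this stands. A reader might infer that proteinuria cannot be detected at any scheduled visit; the documents do not support that. Nor does Appendix 4 word the ratio as a case definition, as it does for proximal tubule dysfunction. It reads as a follow-up rule.

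A reader might also infer that the Day 1 value is useless or that the planned table would be empty. Neither follows. The Day 1 value is the comparator for any for-cause ratio, and only the urine chemistry rows of Table 2.20 lack later data. The display list has no separate change-from-baseline table for urine chemistry, and the 7.1.3 sentence on change from baseline does not name it, so the inconsistency there is one mark in a combined row.

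Finally, the protocol's risk table lists no renal risk, and no primary pharmacokinetic result depends on the ratio. This limits the weight of the point but leaves the gap. Counting coded events does not create a measurement, and one dipstick, eight weeks after the last scheduled injection, cannot supply a ratio.

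**Conclusion.** The narrow point holds: 0 of 15 later schedule columns (17 visits) carry the ratio, while Appendix 4 acts on a change in it. Without a creatinine rise, an abnormal ratio can be found only by a discretionary test. Broad capture of proteinuria remains, through adverse event reports and the single Week 41 dipstick.

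This is worth correcting, at moderate weight. It affects how completely one event of special interest is ascertained and how one part of a laboratory display can be read. It does not affect the pharmacokinetic conclusions or the rest of the safety analysis. The conclusion rests on the current Table 1 as printed and on the creatinine-based reading of estimated GFR stated above.

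**What to change.** Add microalbumin, creatinine and their ratio to Protocol Table 1 at Week 41, where urine is already collected for urinalysis, and add the urine chemistry row to SAP Table 21. The Day 1 baseline then has a scheduled comparator in participants still attending, at most about 40 since that is the number expected to enter the injection phase. Participants who stop early are not covered: the follow-up procedures in Protocol 8.1.3 include no urine test.

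The cost is one extra assay per participant and a minor schedule amendment, with no added visit. This assumes that the specimen's volume and handling suit the assay; the documents do not say.

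If the sponsor declines, four things remain to be done:

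- keep the event of special interest as the SAP counts it, from reported adverse events;
- take urine chemistry out of the change-from-baseline entry in SAP Table 5;
- state in the report that the ratio was not routinely measured after baseline;
- reconcile Table 1 with the Appendix 4 text.

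The event should not be redefined by the Week 41 dipstick alone. That would replace adverse event capture across all visits with a single time point.
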